NCT: NCT04553913
DATE: 10/13/20

Study Title: Proof-of-Concept: A Device to Determine Return of Sensation After a Regional Anesthetic Block.

Principal Investigator, Co-investigator(s): [name] DO; [name]; [name] MD

Sponsor or funding source: Department of Anesthesiology, Wake Forest School of Medicine

Background, Rationale and Context

Regional anesthesia investigators have always shown interest in measuring the specific duration of neuraxial or peripheral nerve blocks, and how variations in block technique or medications affect that duration. Although ostensibly a simple concept, there are many sensory modalities available for block testing (light touch, cold or hot temperature, pain, pressure, etc.) and there is no consensus in the anesthesia literature on how best to measure the duration of nerve block (1). Sensory testing is repetitive, and must be practical and consistent. Pinprick and cold sensation are commonly employed, and these modalities share the same afferent fibers (C-delta) so there is close overlap in the sensory loss mapping after regional block (2). With respect to pinprick sensation (3, 4) there can be variability in the sharpness, pressure, and reproducibility of a pinprick test. Testing for cold sensation may be more consistent, using a controlled stimulus temperature and duration, and there are different methods of testing such as a cooled glass vial (4) (5°C) or Rolltemp (5) (25°C).

Cold therapy is a commonly applied modality following strenuous exercise or during recovery from extremity surgery, and is expected to reduce tissue damage and relieve pain. There is some evidence of benefit but little consensus on the optimum interval and duration of therapy (6), and there are many approved medical devices available for use. This investigation proposes an adaptation of an approved cold therapy device to administer automated, periodic cold stimuli at a location made insensate by regional block. When the patient perceives cold at that site, they will press a stop switch to discontinue cooling which will also stop a timer and give an accurate duration of the time to sensory recovery at that site.

The concept will be tested by comparing the duration measured by this device to the standard measurement of recovery from spinal block employed by post-anesthesia care unit (PACU) nurses who will use pinprick (toothpick) testing of lumbar dermatomes every thirty minutes.

Objectives

Main objective: To test the agreement of standard pinprick (toothpick) sensory recovery testing after spinal anesthesia with the duration of sensory block as determined by the modified device.

Methods and Measures

Design

This is an observational series to determine the agreement of an experimental application of an approved medical device designed to test recovery of sensation from spinal anesthesia, with the customary clinical method of testing recovery from spinal anesthesia.

Subjects selection criteria

- **Inclusion Criteria**
 - Patients 18-75 y/o and scheduled to undergo unilateral primary knee or hip arthroplasty under spinal anesthesia with bupivacaine, ropivacaine or tetracaine will be eligible. The study will be conducted at Wake Forest Baptist Hospital and Davie Medical Center
- **Exclusion Criteria**
 - Exclusions to cold therapy due to medical disease such as Raynaud's disease, Buerger's disease, sickle cell disease, significant peripheral vascular disease (history of limb vascular stents or bypass), hypercoagulable clotting disorders, cold agglutinin disease, history of frostbite of the legs, and neuropathy in the lumbar dermatomes under investigation.
 - Subjects will be excluded if pre-block sensation is abnormal in the L3 dermatome of the non-operative leg, or if spinal anesthesia is not performed or is unsuccessful.
 - Subjects will be excluded if sensation has already returned in the L3 dermatome of the non-operative leg upon arrival to the PACU.
- **Sample Size**
 - Sample size calculations (see analysis below) predict 9 subjects will be sufficient to show equivalence. We will recruit 15 subjects for the study to account for drop-out after enrollment.

Interventions and Interactions

Subjects will be recruited before their surgical date in one of two ways. They may be approached at the conclusion of their preoperative assessment clinic (PAC) appointment to

review the study and provide written consent if willing to participate. If not approached at the PAC visit, they may be contacted by phone prior to the surgical date using a telephone script to introduce the study, review exclusion criteria and determine interest. If interested, subjects will have questions answered and later complete a written informed consent in the preoperative holding area on the day of surgery. The subject's ability to perceive cold (ice) and pain (toothpick) will be assessed in the L3 dermatome on the non-operative thigh, and they will be excluded if pre-block sensation is abnormal in the L3 dermatome, They will also be excluded if decision to use general rather than spinal anesthesia is chosen at this time. If eligibility is confirmed, a skin location on the non-operative thigh will be marked with a circled "X" using marking pen after this assessment to show the location for the device pad to be applied in PACU. Subjects will be shown the cooling device and instructed on how and when to press the "stop" button when they feel cold at the application site.

The patient will then undergo usual anesthesia care with preoperative analgesic and sedative medications, peripheral blocks if indicated, spinal anesthesia and intraoperative sedation. The time of spinal injection and medication and dose will be recorded. Subjects will be excluded at this point if spinal anesthesia is unsuccessful.

After surgery and upon arrival in PACU, if the subject has already recovered sensation at the L3 dermatome (at the "X"), they will be excluded from the study at that time. If they have not recovered sensation, the device pad will be wrapped to the non-operative thigh at the "X" location by a study team member, and an elastic bandage used to secure the cooling pad to the patient. Cycling will begin with 15 min of cold circulation, then 15 minutes off. A PACU nurse who is not aware of the cooling pump activity will test the patient in the lumbar dermatomes (L1 to L4) every 30 minutes per usual practice (the L3 dermatome will be tested adjacent to the cooling pad). The most cephalad level of prick sensation with toothpick stimulus will be recorded on the PACU flowsheet in WakeOne. Cooling pad temperature during pump cycling will be measured with a wireless sensor, and expected to reach approximately 40-50 degrees Fahrenheit when cooling (based on in vitro testing), and return toward body temperature when not cooling; the range will be recorded on the data sheet. Usual PACU discharge criteria will be employed, but it is expected the testing will end when regression of spinal block to L3 is achieved. Study participation will continue until the subject stops the pump cycling, and is expected to continue up to 4 hours.

Outcome Measure(s)

- **Primary Outcome Measure**

Block Recovery Time: Time to resolution of spinal anesthetic (minutes from injection) will be measured in minutes for (i) the device and (ii) standard nursing pinprick testing on the same (non-operative) thigh.

Analytical Plan

Time to resolution of spinal anesthetic will be measured in minutes for (i) our device and (ii) standard nursing pinprick testing on the same (non-operative) thigh. We will test the equivalence of (i) and (ii), where the equivalence region is defined as the difference in (i) and (ii) falling in the interval $[-29, 29]$ minutes. In the sample size calculation, it is assumed that time to spinal resolution has a mean of 140 minutes (standard deviation 29 minutes) such that we are targeting an equivalence region of $[-1, 1]$ standardized units. With type 1 error set to 0.05, we need 9 pairs of observations to achieve 80% power. Calculations were performed using the R package ‘TOSTER’.

To test equivalence of the measurements in real data, the same procedure of “two one-sided tests” will be employed, with t-tests of the one-sided hypotheses that the null difference is less than -29 minutes or that the null difference is greater than 29 minutes.

Human Subjects Protection

Subject Recruitment Methods

Study team members (Anesthesiology Faculty) will be providing the anesthesia care for patients undergoing hip and knee arthroplasty and routinely review clinical information in the days before surgery to prepare for this care. They will identify eligible patients as a part of this review and let the clinical research staff know of potential subject recruitment. Patients meeting eligibility requirements will be recruited before their surgical date in one of two ways. They may be approached at the conclusion of their preoperative assessment clinic (PAC) appointment to review the study and consent form. If not approached at the PAC visit, they may be contacted by phone prior to the surgical date as described above in “interactions” using a telephone script to introduce the study, review exclusion criteria and determine interest. If interested, patients will have questions answered and later complete a written informed consent in the preoperative holding area on the day of surgery. Patients will NOT be recruited on the day of surgery if they have not already been contacted by phone or seen in person prior to their day of surgery.

Informed Consent

Signed informed consent will be obtained from each subject.

Confidentiality and Privacy

Confidentiality will be protected by collecting only information needed to assess study outcomes, minimizing to the fullest extent possible the collection of any information that could directly identify subjects, and maintaining all study information in a secure manner. To help ensure subject privacy and confidentiality, only a unique study identifier will appear on the data collection form. Any collected patient identifying information corresponding to the unique study identifier will be maintained on a linkage file, store separately from the data. The linkage file will be kept secure, with access limited to designated study personnel. Following data collection

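### The 80% power stated for 9 pairs is not met by the planned t-tests and allows for no schedule-driven mean offset, and the charted level does not date L3 recovery

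*Combined protocol and SAP*

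**What the plan says.** The primary outcome is minutes from spinal injection to block resolution, measured once by the device and once by nursing pinprick on the same thigh. In the Analytical Plan, "the equivalence region is defined as the difference in (i) and (ii) falling in the interval" -29 to 29 minutes, tested by two one-sided t-tests (TOST).

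For the sample size, "it is assumed that time to spinal resolution has a mean of 140 minutes (standard deviation 29 minutes"), which the plan turns into a margin of one standardized unit. The Sample Size entry says the calculations "predict 9 subjects will be sufficient to show equivalence"; 15 subjects are to be recruited to cover drop-out. Neither place gives a mean or an SD for the paired difference.

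On timing, Interventions and Interactions says of the device: "Cycling will begin with 15 min of cold circulation, then 15 minutes off". The PACU nurse "will test the patient in the lumbar dermatomes (L1 to L4) every 30 minutes per usual practice". On recording: "The most cephalad level of prick sensation with toothpick stimulus will be recorded on the PACU flowsheet in WakeOne". The nearest the text comes to an L3 endpoint is that "it is expected the testing will end when regression of spinal block to L3 is achieved".

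**The concern.** There are two gaps.

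First, the sample size treats the paired difference as centred on zero with an SD of 29. The centre is unlikely to be zero, because the methods date the same event differently. Pinprick can only be positive at a 30-minute check, so recovery is dated late, by half an interval on average. The device can register recovery whenever the pad is perceptibly cold, so on average it is no later than pinprick and usually earlier. A mean shift towards one margin costs power in an equivalence test. The 29 is also the SD of a recovery time, not of a difference. The two coincide, for equal SDs, only at a within-patient correlation of 0.5.

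Second, the text gives no rule for obtaining the nursing recovery time. As the block regresses downward, L1 recovers before L3. The most cephalad level with prick sensation would then read L1 from the first recovered check onward, whatever happens at L3. Different working rules give different answers: the first positive check lies 15 minutes after the midpoint of its 30-minute interval, about half the margin (15/29 = 0.52).

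**Working it through.** **Inputs.** From the Analytical Plan: margin ±29, one-sided alpha 0.05, power 80%, SD 29, 9 pairs. From Interventions and Interactions: 30-minute checks, 15 minutes on and 15 off. From Sample Size: 15 recruited. Assumed, because the documents do not give them: when the pad is perceptibly cold, and the SD of the paired difference.

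**1. The plan's figure.** Normal approximation, zero mean difference, margin of one SD:

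n = (z0.95 + z0.90)² / 1² = (1.645 + 1.282)² = 8.56, rounded up to 9.

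Power at 9 is 2Φ(√9 − 1.645) − 1 = 82.5%. So 9 reproduces, and zero mean difference is implied though not written.

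**2. The planned test.** TOST succeeds when |d̄| + t(0.95, n−1)·s/√n < 29, with t = 1.860 at n = 9. Integrating over the distribution of s (normal differences, SD 29, mean zero) gives 72% at 9 pairs and 96% at 15. Ten pairs give 79.5%, so 11 are needed for 80%.

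**3. The mean offset.** Suppose both senses return at the same moment, uniformly within a 30-minute cycle, and pinprick is dated at the first positive check.

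- Mean pinprick delay: 30/2 = 15 minutes.
- Mean device delay, with W minutes per cycle without perceptible cold: (W/30)·(W/2) = W²/60.
- Mean device minus pinprick: W²/60 − 15.

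At W = 15 (cold felt exactly during the on phase): 225/60 − 15 = 3.75 − 15 = -11.25. At W = 20: -8.3. At W = 25: -4.6. The limits are -15 (cold always felt) and 0 (felt only momentarily once per cycle). These are means. At W = 15, with the two schedules in random phase, single patients run from -30 to +15.

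**4. Power with the offset.** Same t-based integration; SD is that of the recorded paired difference.

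| SD | Offset | n = 9 | n = 15 | Pairs for 80% |
|---|---|---|---|---|
| 29 | 0 | 72% | 96% | 11 |
| 29 | -11.25 | 50% | 73% | 18 |
| 29 | -15 | 37% | 55% | 28 |
| 20 | 0 | 98% | over 99% | 6 |
| 20 | -11.25 | 78% | 95% | 10 |
| 20 | -15 | 61% | 82% | 15 |
| 15 | 0 | over 99% | over 99% | 5 |
| 15 | -11.25 | 94% | over 99% | 7 |
| 15 | -15 | 82% | 96% | 9 |

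**5. Schedules with no other scatter.** Simulated with identical device and pinprick recovery times: N(140, 29) truncated at an assumed PACU arrival of 80, 100 or 120 minutes, both schedules starting at arrival, W = 15. The recorded difference has mean -11.4 to -12.5 and SD about 11.7. TOST passes at n = 9 in more than 99.9% of trials.

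**The case against.** The strongest reply is that the comparator is nursing pinprick as practised. Background names 30-minute PACU testing, and the Objectives and Design name standard pinprick and the customary clinical method. The offset is then part of what is being compared, not a bias. That stands, and it is why the confirmatory test should stay on raw recorded times. It does not excuse leaving the offset out of the power calculation: a mean shift that belongs to the target still has to be planned for.

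A reader might infer that the two schedules by themselves can make a good device fail. Step 5 rules this out. The loss needs a paired-difference SD of about 20 minutes or more, and the documents report no such figure; 29 enters only because the plan uses it.

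A reader might also infer that nothing limits the conclusion, so that a pass would be taken as proof of accurate sensory recovery time. The Background sentence on accurate duration describes the timer, and the Objectives already confine the comparison to standard pinprick.

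On the L3 rule, it is fair to say that L3 is tested at every check, next to the pad, so the first positive check is the natural reading. But what the text says is charted is a single level, and that level does not carry L3 status. The data collection form is listed in the Appendix and not shown, so an L3 field may exist. The device appendix may likewise give the pad timing.

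**Conclusion.** The point holds in two parts.

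The stated 80% is not what the planned test delivers. At the plan's own SD, t-based power at 9 pairs is 72% with no offset and 50% at -11.25 minutes. All 15 recruits, if evaluable, would give 96% and 73%. At -11.25, 80% power would need 18 pairs, more than will be recruited. The 72% rests only on the plan's inputs and normal differences. The 50% and 73% also assume equal true recovery, dating at the first positive check, and cold felt exactly during the on phase. Other pad timings put the mean offset roughly between 0 and -15. If the SD of the paired difference is 15 or less, the offset matters little.

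Independently of any SD or pad assumption, the charted entry read literally cannot date L3 recovery. On the text shown, the comparator's primary endpoint cannot be derived from it.

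Neither part makes the TOST or its margin invalid.

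**What to change.** 1. In the Outcome Measure section, define the nursing time as the first scheduled check at which toothpick prick is felt at L3, without interpolation. Chart L3 yes/no at every check, unless the data form already does.
2. In the sample-size paragraph, state the assumed mean and SD of the paired difference, and restate t-based power for 9 and 15 pairs at offsets 0 and about -11 minutes, adjusted if the device appendix gives different pad timing.
3. Keep TOST on raw recorded times against ±29 as the confirmatory test.

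The cost is a few sentences and at most one field per check. The L3 field has to be in place before data collection, because a status not charted at the check cannot be reliably recovered later. The downside is that the stated power becomes less favourable and nothing here restores it; the change only shows the limit before the data are seen.

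### The ±29-minute margin for the paired difference is scaled by the SD of a single recovery time, and even if the SD of the difference is 29 minutes the planned t-tests have 72% power at 9 pairs, not 80%.

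*Combined protocol and SAP*

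**What the plan says.** The Analytical Plan compares two times in each patient, both on the non-operative thigh: (i) the device and (ii) nursing pinprick. The margin is placed on their difference: "the equivalence region is defined as the difference in (i) and (ii) falling in the interval $[-29, 29]$ minutes".

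The sample-size input is a different quantity: "it is assumed that time to spinal resolution has a mean of 140 minutes (standard deviation 29 minutes". From it the plan concludes "such that we are targeting an equivalence region of" ±1 standardized units, and then: "With type 1 error set to 0.05, we need 9 pairs of observations to achieve 80% power". The R package TOSTER is named, without function or version.

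The final analysis uses two one-sided tests, "with t-tests of the one-sided hypotheses that the null difference is less than -29 minutes" or more than +29 minutes.

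Under Subjects selection criteria, the Sample Size item says that the calculations "predict 9 subjects will be sufficient to show equivalence". It sets recruitment at 15 to cover drop-out and states no drop-out rate.

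**The concern.** There are two separate problems.

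1. **Wrong SD.** In a paired equivalence test the margin is compared with the standard error of the mean difference, which depends on SD_diff. The plan uses the SD of one recovery time. The documents give no SD_diff, no correlation between the methods and no assumed true mean difference.
2. **Wrong reference distribution.** The 9 pairs matches a normal approximation, but the analysis uses t-tests. With 8 degrees of freedom the difference is not negligible.

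The Sample Size item relies on the 9 and treats the other 6 recruits as spare. Losses after enrolment are foreseen: abnormal pre-block sensation, a switch to general anesthesia, a failed spinal, or sensation already back on arrival in PACU. Ending near 9 evaluable pairs is therefore an outcome the plan accepts. A failure to show equivalence could then be read as disagreement between the methods when it reflects low power.

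**Working it through.** **Inputs from the documents.** Margin 29 minutes on the difference; SD 29 minutes (single time); type 1 error 0.05, taken as 0.05 for each one-sided test; 80% power; 9 pairs; 15 recruited; one-sided t-tests.

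**Inputs not in the documents.** The true mean difference is taken as 0 unless stated. The correlation rho is varied, with both methods given SD 29.

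**Step 1: reproduce the 9 pairs.** The normal-approximation TOST formula with true difference 0 and standardized margin d = 29/29 = 1 is

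n = (z₀.₉₅ + z₀.₉₀)² / d² = (1.645 + 1.282)² / 1 = 8.56, rounded up to 9.

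The approximate power at n = 9 is 2Φ(√9 − 1.645) − 1 = 82.5%. The stated figure is reproduced, but with a z-test.

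**Step 2: power of the planned t-tests, granting SD_diff = 29.** Equivalence is declared when |mean difference| + t₀.₉₅,ₙ₋₁ · s/√n < 29. Exact power comes from integrating over the distribution of s:

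| Pairs | Normal approximation | t-tests (exact) |
|---|---|---|
| 9 | 82.5% | 72.5% |
| 10 | 87.1% | 79.5% |
| 11 | 90.5% | 84.9% |
| 15 | 97.4% | 95.8% |

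A simulation of 1,000,000 trials at 9 pairs also gave 72.5%. Eleven pairs is the first number to reach 80%.

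**Step 3: what the SD of the difference could be.** With equal SDs of 29,

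SD_diff = 29·√(2(1 − rho)).

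This equals 29 only when 2(1 − rho) = 1, that is rho = 0.5. If the second method's SD were 20 or 40 instead of 29, the matching rho would be 0.34 or 0.69. Exact t-based power over assumed rho:

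| rho | SD_diff (min) | 9 pairs | 11 pairs | 15 pairs | Pairs for 80% |
|---|---|---|---|---|---|
| 0 | 41.0 | 28% | 42% | 66% | 19 |
| 0.25 | 35.5 | 46% | 62% | 83% | 15 |
| 0.5 | 29.0 | 72% | 85% | 96% | 11 |
| 0.7 | 22.5 | 94% | 98% | >99% | 7 |
| 0.9 | 13.0 | >99% | >99% | >99% | 4 |

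The largest SD_diff that still gives 80% is 27.1 minutes at 9 pairs (rho about 0.56), 30.5 at 11 (rho 0.45) and 36.5 at 15 (rho 0.21). By the normal approximation, 9 pairs would tolerate 29.7 minutes (rho 0.47).

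**Step 4: a non-zero true difference.** With SD_diff 29 and an illustrative true difference of 5 minutes, power is 67% at 9 pairs and 92% at 15. At 10 minutes it is 54% and 78%.

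**The case against.** The strongest reply is that the study is probably better powered than the tables suggest. Both times run from one spinal injection in one patient and are read on the same thigh, with pinprick at L3 tested next to the pad. Differences between patients in block duration largely cancel in the paired difference, so rho near 0 is implausible and the single-time SD may be conservative.

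A simple model illustrates this. Suppose cold and prick return together and the only discrepancy comes from 30-minute nurse checks and the 15-on/15-off cycle, with independent phases and instant cooling. SD_diff is then about 10 minutes with a mean difference of about −11 minutes, and power at 9 pairs exceeds 99%. Adding independent physiological disagreement of SD 10, 15 or 20 minutes gives about 96%, 85% or 70% at 9 pairs; the last becomes 90% at 15.

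Also, 15 patients are recruited, so with SD_diff 29 and true difference 0 up to 4 can be lost before power falls below 80%. And the 9 is not an arithmetic slip: it follows from a recognised approximation.

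Much of this stands. The direction of the scaling error is unknown, and it may well be favourable. But the model rests on assumptions that the plan does not make. The Background's remark on similar sensory mapping for cold and pinprick gives no correlation of recovery times. The 15 are presented as a drop-out allowance, so they do not support the claim made for 9. The t-test shortfall needs no assumption about rho once the plan's own ±1 standardized region is granted.

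**Conclusion.** The concern holds. The plan standardizes a margin for a paired difference by the SD of a single time, and the SD that determines power is missing. If SD_diff is 29, as the ±1 standardized region implies, the planned tests have 72.5% power at 9 pairs, 7.5 points short of 80%, and need 11 pairs. This rests on a true difference of 0, normally distributed differences and 0.05 for each one-sided test.

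For other values of SD_diff, actual power at 9 pairs may be well below or well above 80%; the documents do not settle which. The claim that 9 subjects suffice is unsupported as written. The consequence is moderate: recruiting 15 cushions the shortfall at SD_diff 29, and no change to the margin or the test is required.

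**What to change.** In the Analytical Plan:

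- State and justify an assumed SD of the device-minus-pinprick difference (or both methods' SDs and their correlation), and state the assumed true difference.
- Replace the claim of 80% power at 9 pairs with exact t-based TOST power at 9, 11 and 15 pairs. A short table over SD_diff of about 13 to 41 minutes, at true differences of 0 and, for example, 10 minutes, would do. At the least, give one sentence with the assumed SD_diff, the assumed true difference and the t-based number of pairs.
- Delete the ±1 standardized region, or say that it assumes SD_diff = 29 (rho = 0.5 with equal SDs).

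In the Sample Size item, change the 9 to match: 11 evaluable pairs if SD_diff is 29 and the true difference is 0.

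Keep the ±29-minute margin, the t-tests and recruitment of 15.

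The cost is rewording in two places and a small table, with no added patients. The power statement becomes a range that is less favourable at low correlation, and at SD_diff 29 the drop-out allowance falls from 15 − 9 = 6 to 15 − 11 = 4.

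### Nine pairs do not give 80% power for the planned t-based equivalence test: the plan's own inputs give about 72%, and 80% needs 11 pairs

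*Combined protocol and SAP*

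**What the plan says.** The Analytical Plan defines equivalence in minutes: "the equivalence region is defined as the difference in (i) and (ii) falling in the interval $[-29, 29]$ minutes", where (i) is the device and (ii) is nursing pinprick testing on the same thigh. For planning, "it is assumed that time to spinal resolution has a mean of 140 minutes (standard deviation 29 minutes", mean and standard deviation together, and on that basis "we are targeting an equivalence region of $[-1, 1]$ standardized units". The result follows: "With type 1 error set to 0.05, we need 9 pairs of observations to achieve 80% power". The R package TOSTER is named as the tool.

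The plan then says that the real data will be analysed by the same two one-sided tests procedure, "with t-tests of the one-sided hypotheses that the null difference is less than -29 minutes" or above +29 minutes.

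The Sample Size entry under the selection criteria repeats the number: "Sample size calculations (see analysis below) predict 9 subjects will be sufficient to show equivalence". It sets recruitment at 15 to cover drop-out. No expected drop-out rate, true mean difference or standard deviation of the paired difference is given.

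**The concern.** The power statement describes a paired, t-based equivalence test on 9 differences, which has 8 degrees of freedom. At that size the gap between a normal and a t calculation is not negligible. The t critical value is larger, and the standard deviation must be estimated from nine values, so some samples give an interval too wide to fit inside the margin even when the true difference is zero. A count of 9 that falls out of the normal formula therefore looked too small for the test specified.

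This figure is the only power statement for the primary analysis, and it sets the floor below which the study is taken to be too small. Patients can be lost after consent for several listed reasons: abnormal L3 sensation before the block, a switch to general anesthesia, an unsuccessful spinal, or sensation already back on arrival in the PACU. If the floor is wrong, so is the number of losses the study can absorb.

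**Working it through.** **Inputs**

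| Input | Value | Source |
|---|---|---|
| Margin | ±29 minutes | Analytical Plan |
| SD used to standardize | 29 minutes, so margin/SD = 1 | Analytical Plan |
| Type I error | 0.05, read as 0.05 per one-sided test | Analytical Plan; per-test reading is the usual one |
| Target power | 80% | Analytical Plan |
| Test | two one-sided t-tests on paired differences, n − 1 df | Analytical Plan |
| True mean difference | 0 | not stated; assumed, most favourable case |

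**Step 1: reproduce the stated 9.** For a paired equivalence test with known SD and zero true difference:

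n = (z₀.₉₅ + z₀.₉₀)² / (margin/SD)² = (1.645 + 1.282)² / 1² = 8.56, rounded up to 9.

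The second quantile is z₀.₉₀ because the 20% type II error is split between the two bounds. Normal-theory power at 9 is 2Φ(√9 × 1 − 1.645) − 1 = 2Φ(1.355) − 1 = 82.5%.

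The other readings tried do not give 9:
- type II error not split: 6.18, so 7;
- 0.025 per side: 10.51, so 11;
- 0.025 per side, type II error not split: 7.85, so 8;
- two independent samples: 17.1, so 18 per group.

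**Step 2: power of the test that is planned.** With D̄ the mean difference and S the sample SD of the differences, equivalence is declared when

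|D̄| < 29 − t₀.₉₅,ₙ₋₁ × S/√n.

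Power is the probability of this event, found by integrating over the distribution of S with σ = 29 and true difference 0.

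To see the effect at n = 9, put S at 29. The t-test needs |D̄| below 29 − 1.860 × 29/3 = 11.0 minutes. The normal formula would allow 29 − 1.645 × 29/3 = 13.1 minutes. Sampling variation in S is a further departure from the known-SD formula.

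| Evaluable pairs | Normal approximation | Exact t-based power |
|---|---|---|
| 9 | 82.5% | 72.5% |
| 10 | 87.1% | 79.5% |
| 11 | 90.5% | 84.9% |
| 15 | 97.4% | 95.8% |

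A simulation of 1,000,000 trials per sample size gave 72.5%, 79.6% and 84.9% at 9, 10 and 11 pairs. The noncentral-t approximation gives 72.4% at 9.

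**Step 3: consequences.** At 9 pairs the shortfall is 80 − 72.5 = 7.5 percentage points, and type II error is 27.5%. The smallest sample with at least 80% power is 11. Of 15 recruited, the tolerable loss is 15 − 11 = 4 (27%), not 15 − 9 = 6 (40%).

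**The case against.** The strongest reply is that 9 is only a floor. The study recruits 15, and on the same inputs it has 95.8% power if all are evaluable and at least 80% with 11 or more. The documents do not show that losses of 5 or 6 are likely. In patient numbers the gap is two, and 10 pairs all but reach the target. Nor is 9 a slip of arithmetic: it is the correct output of a recognised approximation. All of this stands, and it limits the practical harm. It does not make the 80% true of 9 pairs, and a loss of 6 is what a floor of 9 with recruitment of 15 permits.

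The second reply is that 72.5% is itself conditional. The plan gives 29 minutes as the SD of the recovery time, not of the paired difference. If both methods have that SD and correlate at ρ, the SD of the difference is 29√(2(1 − ρ)), which equals 29 only at ρ = 0.5. The documents give no ρ, so these values are assumed:

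| Assumed ρ | SD of difference (min) | Power at 9 | Power at 11 | Power at 15 |
|---|---|---|---|---|
| 0 | 41.0 | 28% | 42% | 66% |
| 0.25 | 35.5 | 46% | 62% | 83% |
| 0.5 | 29.0 | 72.5% | 85% | 96% |
| 0.6 | 25.9 | 84% | 93% | 99% |
| 0.75 | 20.5 | 97% | 99% | about 100% |

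An SD of the difference near 27 minutes would bring 9 pairs to 80%. This is a fair reason to attach conditions to any restated figure. It does not rescue the present statement, because the plan fixes the margin at ±1 standardized unit and so commits itself to 29 minutes for the difference. The zero true difference used here is also generous: at an assumed 5 minutes, power at 9 pairs is 67%, and at 10 minutes 54%.

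**Conclusion.** The concern holds. The stated 80% belongs to a normal approximation, not to the t-tests that the plan specifies. The defect is a mismatch between the planning formula and the analysis. The power figure at 9 pairs and the claim that 9 subjects suffice are both wrong as written.

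The result rests on a margin of ±29 minutes, an SD of the paired difference of 29 minutes, 0.05 per one-sided test and a true mean difference of zero. The first three are the plan's own, on the usual reading of its type I error; the last is the assumption most favourable to the plan. Whether 29 minutes is a sound SD for the difference is a separate question and could move power much further in either direction. The study as recruited is adequately powered on these inputs provided at least 11 patients are evaluable.

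**What to change.** Change two sentences.

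- **Analytical Plan.** State that, for the t-based two one-sided tests with a margin of ±29 minutes, an SD of the paired difference of 29 minutes, a true mean difference of zero and 0.05 per test, 9 evaluable pairs give about 72% power and 11 are needed for at least 80% (85% at 11).
- **Sample Size.** Replace 9 with 11 evaluable pairs, keep recruitment at 15, and describe the drop-out allowance as 4 of 15 (27%). Remove the wording that the number will suffice to show equivalence; power is a probability under assumptions, not an assurance of the result.

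Recruitment, margin, test and procedures are unchanged. The only cost is a less favourable stated figure and a tighter limit on losses. If the investigators expect more than 4 losses, the corrected text will show that 15 is too few on these inputs.
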